17. DATA ANALYSIS PLAN

The primary endpoint of this study is feasibility. We hypothesize that the challenges of enrolling and randomizing AIS patients to a therapeutic intervention within less than one hour of ED presentation can be addressed. The number of potential subjects meeting the inclusion criteria and the relative rates of enrollment over time will be tracked. Additionally, the timing to enrollment and initiation of treatment intervention will be monitored. The primary endpoint of this study is feasibility as measured by the mean time from presentation to the ED to randomization and initiation of intervention. We hypothesize that we will be able to enroll, randomize and initiate treatment intervention in less than one hour for 80% of the enrolled subjects.

This study is not powered to detect significant differences in secondary or exploratory outcomes. However, analysis of secondary outcomes will occur both on an intention-to-treat and a per-protocol basis. Penumbral salvage will be reported as an average and as a standard deviation of the mean. We plan to enroll a total of 200 patients. Based on previous data that showed a decrease in the relative infarct volume growth (infarct volume at presentation/infarct volume at 4 hours) in patients treated with hyperoxia (87.8 +/-22%) compared to controls (149.1 +/- 41%)²⁹, 5 patients per arm would be needed to detect a similar difference with a power of 90% and type I error rate (α) of 0.05⁶². However, this effect was seen in a small study with less than 10 patients per treatment arm. Thus, such dramatic changes in infarct volume may not be expected, but even a smaller reduction in infarct volume will be clinically important as small reductions in infarct volume can have profound clinical effects if it is in a key cerebral territory. If you assume 20% of patients for some reason do not receive standard follow-up imaging to allow for calculation of infarct progression, a standard deviation of 41%, 80% power and α of 0.05, the proposed sample size will be able to detect an absolute difference in infarct volume growth of 18% between the control and hyperoxia.

In terms of effects on clinical patient outcomes, both the effect on 3-month mRS and NIHSS will be determined. The DEFUSE-3 study found the median NIHSS score in AIS patients evaluated for possible extended-window thrombectomy was 16 with an interquartile range of 10-20⁶³. Based on these results and our proposed sample size for feasibility and a 29% loss to follow-up, we will be able to detect a two-point difference in NIHSS between the hyperoxia and control groups at 24hours with 80% power and a type I error (α) of 0.05. Given the large potential number of confounding events between the time of study intervention and a 3-month mRS, this will be analyzed on an exploratory basis. The average 3-month mRS in both the hyperoxia and control groups will be compared. Finally, an exploratory analysis of the effects of hyperoxia on biomarkers of stroke severity and hyperoxic lung injury will be evaluated over time. The change in level of biomarkers (MMP-9, IL-6, and IL-8) over time will be analyzed and reported using the mean and standard deviation and will be depicted graphically.

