The primary study outcome is to determine the feasibility of enrolling and randomizing AIS patients to a therapeutic intervention within less than one hour of ED presentation. Secondary outcomes of potential therapeutic effect to inform future clinical trial(s) include penumbral salvage at repeat imaging, change in NIHSS over the first 24 hours, and 3-month mRS. To assess potential adverse effects on markers of worsening stroke severity and possible hyperoxic lung injury, levels of MMP-9, IL-6, and IL-8 will be measured at initiation, 4 hours and 24 hours. Further analysis of additional biomarkers will be considered in the future.

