4.3. STUDY INTERVENTIONS

Enrolled subjects will be randomized to receive either brief hyperoxia treatment (defined as 15L/min supplemental oxygen) or medical air (at 15L/min) via a partial non-rebreather mask for four hours from the time of study initiation (T_1). Supplemental oxygen is routinely used to correct and/or prevent hypoxemia (low blood oxygen content, defined as an arterial oxygen content of less than 60-75mmHg). To avoid invasive monitoring of arterial oxygen content, pulse oximetry is routinely used to monitor for hypoxia with values less than 90-94% considered low in most clinical scenarios. Unfortunately, there are limitations with pulse oximetry and based on the oxyhemoglobin dissociation curve and a SpO_2 of 97% could represent any PaO_2 above ~90mmHg. Thus, pulse oximetry alone is not an ideal mechanism to determine hyperoxia. Based on mouse models, this study targets a PaO_2 of 200-400mmHg in the hyperoxia treatment group. In a previous study of cardiac catheterization patients, delivery of 10-15L/Min facemask oxygen resulted in average PaO_2 in the 400s.

In this study, oxygen is being used as a drug. However, an IND exemption is requested. We feel that the use of oxygen in this scenario to prevent hypoxemia in the ischemic tissue by creating a global hyperoxia environment meets the criteria for an IND exemption. Specifically, this protocol will: be conducted in compliance with requirements for IRB review and the requirements concerning the promotion and sale of drugs; not be in support of a new indication for use or change in labeling or advertising of oxygen; not invoke exemption from informed consent; not involve a route of oxygen administration or dosage level that significantly increase the risks of the drug product. Additionally, there is no consistent predetermined dosage of oxygen that can be universally applied to all clinical contexts to determine who needs supplemental oxygen and at what dose. This decision is left to the clinical judgement of the practicing medical provider. For example, in patients undergoing procedural sedation in the ED, supplemental oxygen may be provided despite having a pulse oximetry reading greater than 92-94% to prevent desaturation. According to the AHA guidelines for stroke patients, hypoxia that they suggest warrants supplemental oxygen use is defined as a pulse oximetry of less than 94%, but the data behind this exact recommendation is also very weak⁵⁰.

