6. CONSENT PROCESS

Upon identification of a subject meeting all inclusion and no exclusion criteria, subjects will be approached by study research personnel (either the PI or a Research Assistant) to obtain informed consent prior to initiation of any study activities. This will occur while patients are in the ED and under the primary care of the ED physician. Given the goal of randomization within one-hour of presentation to the ED, care will be taken to not interfere with ongoing medical care while still ensuring timely approach for enrollment. Consent forms describing in

appropriate detail the study interventions, study procedures, and risks will be given to the participant and/or their LAR. Consent forms will be Institutional Review Board (IRB)-approved and the subject/LAR will be asked to read and review the document. A verbal explanation will also be provided in terms suited to the subject's comprehension of the purposes, procedures, and potential risks of the study and of their rights as research participants. Participants will have the opportunity to carefully review the written consent form and ask questions prior to signing. The participants will have the opportunity to discuss the study with their family or surrogates and think about it prior to agreeing to participate. The participant/LAR will sign the informed consent document prior to any study procedures being done. Subjects/LARs will be informed that participation is voluntary and that they may withdraw from the study at any time, without prejudice. A copy of the informed consent document will be given to the participants for their records. The informed consent process will be conducted and documented in the source document (including the date), and the form signed, before the participant undergoes any study-specific procedures. A witness signature will be not be included on the consent form. However, a signature of the study personnel completing the consent is included and required. The rights and welfare of the participants will be protected by emphasizing to them that the quality of their medical care will not be adversely affected if they decline to participate in this study.

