When the patient's capacity for informed consent is questioned due to the nature of the stroke itself or other mental impairment, capacity will be determined using the UABCC Form. This method of determining capacity consists of a 10-item questionnaire that can be delivered in 5-10 minutes and has been found to have high sensitivity and specificity and good interrater reliability⁵³. If a subject is determined to not have capacity for consent, the LAR will be identified and approached for consent. If and when the study subject regains capacity, they will be approached for continued participation. If the subject/LAR consents for participation he/she will sign the informed consent document prior to any procedures being done specifically for this study.

After a patient consents for participation in the study, he/she will be randomized to either hyperoxia or medical air treatment. Randomization will occur in blocks of 20 using excel and subject treatment assignments will be determined prior to initiation of the study and enrollment of subjects.

In addition to the traditional paper consent process, the ongoing COVID-19 pandemic has necessitated the use of an optional electronic consent (eConsent) process. Bringing a paper consent form and pen to the bedside of a patient with known or suspected COVID-19 and then taking these out of the room would violate infection control principles and policies. Additionally, the current pandemic presents challenges to obtaining consent from the LAR who may not be physically present in the ED at the time of consent due to a variety of reasons including limited visitation policies and/or the need to self-quarantine. Therefore, an eConsent process will also be used. In these cases, if a subject has decisional capacity and/or the LAR is physically present in the ED, but there is concern for COVID-19 infection, the research team will call the subject on their hospital room phone or personal phone and request to email the subject/LAR a copy of the eConsent form. The same process for informed consent, including explanation of the consent process and study, and opportunity for questions, will occur via telephone. At the end of the conversation, the subject/LAR will be asked to complete the eConsent Survey via REDCap. The research team and witness signatures will also be documented via REDCap. The same process will be used if the subject lacks decisional capacity and the LAR is not physically present in the ED for consent.

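### The primary feasibility endpoint is measured by a mean time, but the only quantified feasibility target is a proportion (under one hour for 80% of enrolled subjects), so the stated measure does not test the stated hypothesis

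*Combined protocol and SAP*

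**What the plan says.** Section 17 (Data Analysis Plan) names feasibility as the primary endpoint and gives its measure: "feasibility as measured by the mean time from presentation to the ED to randomization and initiation of intervention". It gives this mean no limit, confidence interval or test. The sentence that follows states the hypothesis in another form, namely that the team can enroll, randomize and "initiate treatment intervention in less than one hour for 80% of the enrolled subjects". Earlier in the same section, "the timing to enrollment and initiation of treatment intervention will be monitored", but with no criterion.

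Two other sections carry the one-hour figure without a percentage or a summary statistic. Section 4 (Study Design) gives the primary outcome as the "feasibility of enrolling and randomizing AIS patients to a therapeutic intervention within less than one hour of ED presentation". Section 6 (Consent Process) says "Given the goal of randomization within one-hour of presentation to the ED". Both stop the clock at randomization, whereas Section 17 stops it at randomization and initiation of the intervention.

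Target enrollment is 200 (Sections 4.1 and 17).

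**The concern.** A mean and a proportion below a cut-off are different quantities, and the first does not determine the second unless the spread and shape of the times are known. Reported as written, the primary result would be a number of minutes, while the hypothesis asks what share of subjects was started in time. No sentence says which of the two decides feasibility, so that choice could be made after the data are seen.

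The stakes are practical. Section 17 disclaims power for the secondary outcomes, so feasibility is the main product of this trial. Section 2 says the project will inform the design of a later one. A trial of early treatment needs to know what fraction of enrolled patients can be started within the hour. A mean can look reassuring while that fraction falls short.

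The two measures also treat subjects who never start differently. Such a subject has no start time to average, but counts against a target expressed as a share of those enrolled.

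**Working it through.** **1. Is there a figure to reproduce?** No. Section 17's sample-size and detectable-difference figures concern infarct growth and NIHSS. The plan gives no power or precision for the primary endpoint and no mean, standard deviation or distribution for the time to start. The distributions below are therefore assumptions, shown over a range.

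**2. Share under 60 minutes implied by a given mean.** Let m be the mean and CV the standard deviation divided by the mean.

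- Lognormal: σ² = ln(1 + CV²), μ = ln(m) − σ²/2, share = Φ((ln 60 − μ)/σ).
- Gamma: shape 1/CV², scale m·CV², share = the distribution function at 60.

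Example, lognormal with m = 55 and CV = 0.3: σ = 0.2936, μ = 4.0073 − 0.0431 = 3.9642, (4.0943 − 3.9642)/0.2936 = 0.443, and Φ(0.443) = 67.1%.

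Share under 60 minutes, lognormal / gamma:

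| Mean (min) | CV 0.2 | CV 0.3 | CV 0.45 | CV 0.6 |
|---|---|---|---|---|
| 45 | 94.0% / 94.2% | 87.0% / 86.5% | 81.2% / 79.3% | 78.7% / 75.8% |
| 50 | 84.6% / 84.3% | 77.9% / 76.6% | 73.9% / 71.4% | 72.8% / 69.6% |
| 55 | 70.5% / 69.4% | 67.1% / 65.3% | 66.2% / 63.5% | 66.8% / 63.6% |

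At a mean of 55 minutes the 80% target is missed in every cell. At 50 minutes it is met with CV 0.2 and missed with CV 0.3 or more, so the same mean gives opposite answers.

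**3. Mean at which exactly 80% are under 60 minutes.** For the lognormal, m = 60·exp(σ²/2 − 0.8416σ). With CV = 0.2, σ = 0.1980 and m = 60·exp(0.0196 − 0.1667) = 51.8. The gamma values were solved numerically.

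| CV | Lognormal | Gamma |
|---|---|---|
| 0.2 | 51.8 min | 51.6 min |
| 0.3 | 48.9 min | 48.4 min |
| 0.45 | 45.8 min | 44.6 min |
| 0.6 | 43.9 min | 41.7 min |

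**4. The reverse case.** Suppose the timely 80% average 45 minutes (assumed). The mean exceeds 60 once the late 20% average more than (60 − 0.8 × 45)/0.2 = 120 minutes. With the late fifth at 150 minutes, the mean is 0.8 × 45 + 0.2 × 150 = 66 minutes with the target met.

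**5. Precision of the proportion.** With 200 enrolled, 160/200 = 80% has an exact (Clopper-Pearson) 95% confidence interval of 73.8% to 85.3%.

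**The case against.** The best defence is that the two sentences belong together: the mean describes the interval, and 80% within the hour is the target. That is a sensible intention, but it is not what is written. The words that define the measure are attached to the mean, and no analysis of the proportion follows.

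A reader might infer that the mean has no benchmark at all. That goes too far, because the one-hour figure appears in Sections 4, 6 and 17. A reader might equally infer that success is a mean under 60 minutes. The plan does not say so, and step 2 shows that this would not test the 80% hypothesis.

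The reverse case should not be pressed. Delay is conceivable where "If a subject is determined to not have capacity for consent, the LAR will be identified and approached for consent", but the documents give no data on such delays, and Section 6 provides remote electronic consent when the representative is absent. Table 1 in Section 7 puts consent and randomization in a column with a window of 60 minutes around ED arrival, which makes large delays to randomization less likely. It is a schedule window rather than an eligibility limit, and it does not bound the gap from randomization to start, so the case remains possible.

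A reader might also infer that subjects who never start will be dropped, by some known amount. The documents do not support a figure. Section 4.3 says "Enrolled subjects will be randomized to receive either brief hyperoxia treatment", which puts enrollment before randomization but does not equate it with consent, and Section 5 lists consent, enrollment and initiation separately. Replacement is described in both Section 4.1 and Section 13, so the final denominator cannot be worked out.

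It also stands that no data are lost: both summaries come from times already being monitored.

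**Conclusion.** The concern holds. The stated measure of the only primary endpoint does not answer the only quantified feasibility hypothesis, and the plan does not say which governs. This follows from the text alone; the arithmetic shows that the gap can matter. Under lognormal or gamma times with CV 0.2 to 0.6, a mean of 55 minutes leaves about 64% to 71% under the hour, and the 80% target corresponds to a mean of about 42 to 52 minutes. These figures rest on assumed distributions, and no single mean can stand in for the target.

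One might read the 80% hypothesis as a go/no-go rule requiring an observed share of at least 80%. The plan states no such rule, so none should be attributed to it. The defect is one of definition. It should be put right before the analysis, and it does not call the conduct of the trial into question.

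**What to change.** In Section 17, replace the mean as primary measure with the proportion of enrolled subjects in whom the intervention was started less than 60 minutes after ED presentation. Report it with an exact 95% confidence interval against the 80% target, and give mean and median (interquartile range) time as supportive. The sponsor should also:

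- state who counts as enrolled, and count enrolled subjects who never start as not meeting the target;
- choose any formal success rule in advance. With 200 enrolled, requiring an observed 80% (160/200) passes with probability 6%, 54% and 98% at true rates of 75%, 80% and 85%. Requiring evidence of more than 80% at one-sided 0.025 needs 172/200 and has power 39% at a true 85% and 97% at 90%. The documents do not indicate which, if either, is meant;
- use the same clock stop in Sections 4, 6 and 17.

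The cost is wording in those sections and keeping enrolled non-starters in the count. Sample size and procedures are unchanged. The downside is that the headline may look less favourable than a mean.

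### Section 17 calls the secondary outcomes unpowered yet claims 80% power for two of them; the NIHSS figure does not reproduce, and neither intention-to-treat nor per-protocol leads

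*Combined protocol and SAP*

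**What the plan says.** The primary endpoint is feasibility. Section 4 (Study Design) names the outcomes that speak to benefit: they "include penumbral salvage at repeat imaging, change in NIHSS over the first 24 hours, and 3-month mRS", and their purpose is to inform later trials.

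Section 17 (Data Analysis Plan) then makes four statements that bear on how those outcomes will be read.

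- On power in general: "This study is not powered to detect significant differences in secondary or exploratory outcomes".
- On infarct growth, assuming 20% without follow-up imaging, an SD of 41%, 80% power and alpha 0.05: "the proposed sample size will be able to detect an absolute difference in infarct volume growth of 18% between the control and hyperoxia".
- On NIHSS, citing a median of 16 and interquartile range of 10 to 20 from a thrombectomy trial, 29% loss to follow-up and alpha 0.05: "we will be able to detect a two-point difference in NIHSS between the hyperoxia and control groups at 24hours with 80% power".
- On populations: "However, analysis of secondary outcomes will occur both on an intention-to-treat and a per-protocol basis".

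For mRS, Section 17 says "this will be analyzed on an exploratory basis". The biomarkers get the same exploratory label; imaging and NIHSS do not. The documents do not rank the two populations, define the per-protocol set, name a lead secondary outcome or say how several outcomes are to be read together.

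**The concern.** The feasibility endpoint compares nothing between arms, so what the trial says about clinical or imaging benefit will come from these secondary outcomes. Their status is contradictory: unpowered in one sentence, given 80% power in later ones. A reader of the results could not tell whether a null comes from an adequately sized comparison.

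The populations raise a similar difficulty. If intention-to-treat and per-protocol disagree, nothing says which stands. Any per-protocol set built on adherence depends on events after randomization. Section 13 allows the intervention to be stopped for non-compliance or adverse events, and Section 4 concedes that full blinding cannot be guaranteed. Such a set may lose the balance that randomization provides.

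At stake is the design of the next trial, which these results are meant to guide.

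**Working it through.** Sidedness is not stated, so two-sided 0.05 is assumed. The multipliers are 1.96 for alpha and 0.842 for 80% power, 2.80 in total.

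**1. Infarct growth (the plan's own figure)**
- Inputs from Section 17: 200 enrolled in equal arms, 20% without imaging, so 100 × 0.80 = 80 per arm; SD 41.
- Standard error = 41 × √(2/80) = 6.48.
- Detectable difference = 2.80 × 6.48 = 18.2, or 18.3 using the t distribution.
- The stated 18% reproduces as a two-sided 0.05 comparison. Power at exactly 18 is about 79%.

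**2. NIHSS at 24 hours**
- Inputs from Section 17: interquartile range 10 to 20; 29% loss, so 100 × 0.71 = 71 per arm.
- SD if normal = (20 − 10)/1.349 = 7.41.
- Standard error = 7.41 × √(2/71) = 1.244.
- Detectable difference = 2.80 × 1.244 = 3.49 points, not 2.
- Power for 2 points = Φ(2/1.244 − 1.96) = Φ(−0.35) = 36%.
- One-sided at 0.05, the detectable difference is 3.1 points and the power 49%, so sidedness does not explain the gap.
- SD needed for 80% power at 2 points = 2/(2.80 × √(2/71)) = 4.25.

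Baseline adjustment could reach an SD of 4.25 only if baseline and 24-hour scores were highly correlated: √(1 − r²) = 4.25/7.41 = 0.574 gives r ≈ 0.82. Section 17 gives no such correlation and names no adjusted model.

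**3. Chance of at least one nominal p<0.05 when there is no effect**

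The documents give no correlations, so these are simulated ranges (1,000,000 draws, each comparison two-sided at 0.05). Correlation between outcomes was varied from 0 to 0.8. Correlation between the two populations was either set at 0.8 to 0.95 or derived from a per-protocol share of 70-95% of subjects.

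| Comparisons | Chance rate |
|---|---|
| One outcome, both populations | 6.0-7.8% |
| Two outcomes, intention-to-treat only | 7.8-9.75% |
| Two outcomes, both populations | 10-15% |
| Three outcomes (mRS counted), both populations | 12.6-21.6% |

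The upper end of the second row is 1 − 0.95² = 9.75%. Most of the excess comes from having several outcomes; the second population adds less.

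**4. Expected precision (95% half-width)**
- Infarct growth: 1.96 × 6.48 = ±12.7 percentage points.
- NIHSS: 1.96 × 1.244 = ±2.4 points.

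**The case against.** The best defence is that this is a feasibility trial, described in Section 4 as gathering preliminary data, with secondary outcomes meant to inform later work. Section 17's opening disclaimer covers imaging and NIHSS, and the later figures can be taken as detectable differences for a sample size set on other grounds. Much of this stands. With no confirmatory efficacy claim, no formal error guarantee is broken, and a prescribed testing order would be a matter of preference.

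Three stronger readings are tempting but not supported.

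- A reader might infer that the secondaries are planned as formal 80%-power tests. Section 17 names no test, significance threshold or success rule for them, and penumbral salvage is to be reported only as a mean and SD.
- A reader might infer a single inflation factor, such as 2.5 times the nominal rate, caused by the two populations. Any single factor needs correlations that the documents do not give, and the two populations alone account for only part of it.
- A reader might infer that per-protocol will drop subjects given added oxygen or stopped for an adverse event, and put a size on the resulting bias. The documents say that such subjects continue their assessments. They do not say who leaves the per-protocol set. The gap is the missing definition.

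The defence does not reconcile the disclaimer with the two power sentences, and it does not rescue the NIHSS figure. It also does not explain why the exploratory label reaches mRS and the biomarkers but not imaging or NIHSS.

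**Conclusion.** The point holds as a conflict within the plan together with one wrong figure. Section 17 cannot both disclaim power for the secondary outcomes and claim 80% for two of them. The 18% infarct-growth figure is sound on its inputs. The two-point NIHSS figure is not: on the inputs quoted beside it, power is about 36% and the detectable difference about 3.5 points.

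The NIHSS result assumes approximate normality, although the quoted quartiles are not symmetric about the median of 16. It also assumes that the spread in that thrombectomy population carries over to this trial, which excludes patients planned for alteplase or endovascular therapy and admits scores from 1 upward. The plan would need to show an SD near 4.25 to keep its claim.

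The unranked populations and the two labels for mRS are real but smaller defects. The 10-15% chance rate is a guide to reading an isolated p<0.05. Naming intention-to-treat as lead would still leave about 8-10% for two outcomes, which is why the hypothesis-generating label is needed as well.

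**What to change.** In Section 17:

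1. Make intention-to-treat (all randomized subjects, as assigned) the lead analysis for every secondary outcome. Define the per-protocol set in advance and keep it as a supportive sensitivity analysis on which no conclusion rests.
2. Label imaging, NIHSS and mRS as hypothesis-generating, reported as between-arm estimates with 95% confidence intervals.
3. Replace the two power sentences with expected precision: about ±12.7 percentage points for infarct growth (80 per arm, SD 41) and about ±2.4 NIHSS points (71 per arm, SD 7.4). If a detectable NIHSS difference is kept, restate it as about 3.5 points, or give the source of a smaller SD.

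In Sections 4 and 17, give 3-month mRS the same status.

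The cost is a few sentences, with no added patients or data. The sponsor gives up presenting an isolated p<0.05, or a result seen only per-protocol, as a detected effect, and the NIHSS figure becomes less favourable.
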